#### 4.2.2.1 Adverse Events

Adverse Events will be collected throughout the study from date of informed consent until the end of the follow-up. The MedDRA will be used to code the AEs using the latest available version.

Treatment-emergent AEs are those AEs with onset date/time at or after dosing.

A listing will cover details for each individual AE including MedDRA SOC, PT, reported term, seriousness, start and stop date/time, relatedness to IMP, intensity (mild, moderate, severe and CTCAE grade 1-5), actions taken, time from last dose, whether or not leading to withdrawal from the study, AESI identification and outcome.

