11 Participants who are symptomatic must be dosed with IMP no more than 7 days from self-reported or observed onset of COVID-19-related symptoms or measured fever, defined as the self-reported date of first reported sign/symptom from the list in [Table 13](#). One or more COVID-19 signs/symptoms must also be present within 24 hours prior to Day 1 to be eligible for inclusion.

12 Oxygenation saturation of \geq 92% obtained at rest by study staff within 24 hours prior to Day 1, unless the potential participant regularly receives chronic supplementary oxygen for an underlying lung condition.

Note that Cohort 2 will only be included if the indication is progressed in adults.

COHORT 3: Participants with severe COVID-19 (treatment):

13 Patients hospitalized with COVID-19 with a time between onset of symptoms and dosing AZD7442 of \leq 7 days

14 Documented positive SARS-CoV-2 RT-PCR test collected \leq 3 days prior to Day 1 or a positive rapid SARS-CoV-2 antigen test at screening.

15 Spontaneous blood ALT/AST levels \leq 5 times the ULN

16 Glomerular filtration rate \geq 30 mL/min/1.73 m²

Note that Cohort 3 will only be included if the indication is progressed in adults.

Route of Administration:

Participants will receive IM AZD7442 unless they meet any of the following criteria for IV administration:

- 17 The participant has severe COVID-19
- 18 IM dosing is contraindicated due to:
 - (a) Thrombocytopenia (< 120000 cells/mm³)
 - (b) Coagulation defects
 - (c) Any other condition that would compromise the absorption of AZD7442 or safety of the participant (eg, hypovolemic shock, myopathy, muscular atrophy, active infection other than SARS-CoV-2, cellulitis, and dermatitis at the injection site).
- 19 Any other participant for whom the enrolling physician considers an IV infusion the most appropriate route of administration.

Informed Consent

- 20 Provision of a signed and dated written informed consent form prior to any mandatory study specific procedures, sampling, and analyses. Informed assent is to be provided by participants who are capable of forming an opinion and assessing the information given to him or her; informed consent must be provided by the participant's legal guardian.

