8.1.2 Severe COVID-19 Criteria

In all cohorts, severe COVID-19 will be characterized by a minimum of either pneumonia (fever, cough, tachypnea, or dyspnea, and lung infiltrates) or hypoxemia ($\text{SpO}_2 < 90\%$ in room air and/or severe respiratory distress) and a WHO Clinical Progression Scale score of 5 or higher ([Table 14](#)). Severe COVID-19 will be collected and recorded in the eCRF as an SAE.

Table 14 WHO Clinical Progression Scale

Patient state	Descriptor	Score
Uninfected	Uninfected, no viral RNA detected	0
Ambulatory mild disease	Asymptomatic; viral RNA detected	1
	Symptomatic; independent	2
	Symptomatic; assistance needed	3
Hospitalized: moderate disease	Hospitalized; no oxygen therapy ^a	4
	Hospitalized; oxygen by mask or nasal prongs	5
Hospitalized: Severe Disease	Hospitalized; oxygen by NIV or high flow	6
	Intubation and mechanical ventilation, $pO_2/FiO_2 \geq 150$ or $SpO_2/FiO_2 \geq 200$	7
	Mechanical ventilation $pO_2/FiO_2 < 150$ ($SpO_2/FiO_2 < 200$) or vasopressors	8
	Mechanical ventilation $pO_2/FiO_2 < 150$ and vasopressors, dialysis, or ECMO	9
Dead	Death	10

^a If hospitalized for isolation only, record status as for ambulatory patient.

ECMO, extracorporeal membrane oxygenation; FiO_2 , fraction of inspired oxygen; NIV, non-invasive ventilation; pO_2 , partial pressure of oxygen; SpO_2 , oxygen saturation, WHO, World Health Organization.
(Marshall et al 2020)

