8.3.2 Follow-up of AEs and SAEs

Any AEs that are unresolved at the participant's last visit in the study are followed up by the Investigator for as long as medically indicated, but without further recording in the eCRF. AstraZeneca retains the right to request additional information for any participant with ongoing AE(s)/SAE(s) at the end of the study, if judged necessary.

Adverse Event Variables

The following variables will be collected for each AE:

- AE diagnosis and description (verbatim)
- The date and time when the AE started and stopped

- Severity grade/maximum severity
- Whether the AE is serious or not
- Investigator causality rating against the IMP(s) (yes or no)
- Action taken with regard to the IMP(s)
- AE caused participant to withdraw from study (yes or no)
- Outcome

In addition, the following variables will be collected for SAEs:

- Date AE met criteria for SAE
- Date Investigator became aware of SAE
- AE is serious due to
- Date of hospitalization (if hospitalized)
- Date of discharge
- Probable cause of death (if death occurred)
- Date of death (if death occurred)
- Autopsy performed (if death occurred)
- Causality assessment in relation to study procedure(s)
- Causality assessment to other medication

The following severity ratings will be used, adapted from the Common Terminology Criteria for Adverse Events version 5.0 ([NIH 2017](#)):

- Grade 1: An event of mild intensity that is usually transient and may require only clinical or diagnostic observations. The event does not generally interfere with usual activities of daily living.
- Grade 2: An event of moderate intensity that is usually alleviated with additional, specific therapeutic intervention, which is minimal, local, or non-invasive. The event interferes with usual activities of daily living, causing discomfort, but poses no significant or permanent risk of harm to the participant.
- Grade 3: A severe event that requires intensive therapeutic intervention but is not immediately life-threatening. The event interrupts usual activities of daily living, or significantly affects the clinical status of the participant.
- Grade 4: An event, and/or its immediate sequelae, that is associated with an imminent risk of death and urgent intervention is indicated.
- Grade 5: Death, as result of an event.

It is important to distinguish between serious and severe AEs:

- Severity is a measure of intensity, whereas seriousness is defined by the criteria in [Appendix B 2](#).

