An AE is the development of any untoward medical occurrence in a patient or clinical study participant administered a medicinal product and which does not necessarily have a causal relationship with this treatment. An AE can therefore be any unfavorable and unintended sign (eg, an abnormal laboratory finding), symptom (for example nausea, chest pain), or disease temporally associated with the use of a medicinal product, whether or not considered related to the medicinal product.

The term AE is used to include both serious and non-serious AEs and can include a deterioration of a pre-existing medical occurrence. An AE may occur at any time, including run-in or washout periods, even if no study intervention has been administered.

B 2 Definition of Serious Adverse Events

An SAE is an AE occurring during any study phase (ie, run-in, treatment, washout, follow-up), that fulfills one or more of the following criteria:

- Results in death
- Is immediately life-threatening
- Requires in-participant hospitalization or prolongation of existing hospitalization
- Results in persistent or significant disability or incapacity
- Is a congenital anomaly or birth defect
- Is an important medical event that may jeopardize the participant or may require medical treatment to prevent one of the outcomes listed above

Adverse events for **malignant tumors** reported during a study should generally be assessed as **Serious AEs**. If no other seriousness criteria apply, the ‘Important Medical Event’ criterion should be used. In certain situations, however, medical judgment on an individual event basis should be applied to clarify that the malignant tumor event should be assessed and reported as a **non-serious AE**. For example, if the tumor is included as medical history and progression occurs during the study, but the progression does not change treatment and/or prognosis of the malignant tumor, the AE may not fulfill the attributes for being assessed as serious, although reporting of the progression of the malignant tumor as an AE is valid and should occur. Also, some types of malignant tumors, which do not spread remotely after a routine treatment that does not require hospitalization, may be assessed as non-serious; examples in adults include Stage 1 basal cell carcinoma and Stage 1A1 cervical cancer removed via cone biopsy.

Life-threatening

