#### Adverse Event of Special Interest

An AESI includes any of the following TEAEs (categorized in the eCRF):

- Anaphylaxis
- Hypersensitivity
- Serious Hypersensitivity Reaction including immune complex disease
- Injection Site and Infusion Site Reactions (as identified by the investigator in the Adverse Event eCRF form. For the summary of injection/infusion site inspection, please see Section 4.2.8.2)
- MIS-C

- Thrombotic events, heart failure and cardiac ischemia

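### The SAP's onset-only TEAE rule leaves out of the TEAE and AESI counts any event with a recorded pre-dose start that worsens or first becomes serious after dosing

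*SAP*

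**What the plan says.** SAP 4.2.2.1 gives the whole rule in one sentence: "Treatment-emergent AEs are those AEs with onset date/time at or after dosing". Under its AESI heading the SAP adds "An AESI includes any of the following TEAEs", so an event must be a TEAE before it can be an AESI. TEAEs, SAEs and AESIs are all primary safety endpoints (SAP Table 2 and 4.2.2).

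The protocol's concept of an adverse event is wider. Appendix B 1 says that an AE "can include a deterioration of a pre-existing medical occurrence". Protocol 8.3.2 collects a start and stop date, a severity grade or maximum severity and, for serious events, a separate field: "Date AE met criteria for SAE". One record can therefore start on one date and become serious on a later one.

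The documents differ on when AE collection begins. Protocol 8.3.1 collects AEs from dosing and SAEs from signature of the consent form. SAP 4.2.2.1 has all AEs collected from consent. Neither document says which onset date a worsening event receives.

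**The concern.** These children enter with illness already present. Cohorts 1 and 2 must be immunocompromised or have a comorbidity that raises the risk of severe COVID-19. For Cohort 2, inclusion criterion 11 allows dosing up to 7 days after symptom onset and adds "One or more COVID-19 signs/symptoms must also be present within 24 hours prior to Day 1 to be eligible for inclusion". In such a population, harm after dosing can appear as worsening of something that began before dosing. Protocol 2.3.1 names antibody-dependent enhancement of disease as a theoretical risk, and in a child who is already infected that could look like existing illness getting worse.

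Under an onset-only rule, the same clinical course is a TEAE if the site dates it from the worsening, and is not a TEAE if the site dates it from the start of the symptom. Two primary safety counts then depend partly on how sites date events.

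**Working it through.** The documents give no figure on this point, so the check is mainly a reading of the rules side by side, with a short calculation for scale.

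**Which events the rule excludes**

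1. *Cohort 2 symptoms.* Protocol 8.1.1 records a listed COVID-19 sign or symptom as an AE in Cohorts 2 and 3 only if it is serious, leads to study discontinuation, or is judged not related to COVID-19. The item recorded is the sign or symptom itself. If it began before dosing and became serious afterwards, its start date can be pre-dose, and the rule then excludes it.
2. *Onset between consent and dosing.* Screening runs from Day -7 to Day 1. SAEs in that window are recorded under both documents; non-serious AEs are recorded only under the SAP's wording. None becomes a TEAE, even if it worsens after dosing.
3. *Dating by the site.* If worsening of a known condition is entered under the existing start date, the event is excluded. If it is entered as a new event, it is included.

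**Whether another SAP provision closes the gap**

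- SAP 3.3.5 imputes missing start dates. It does not change a known pre-dose date.
- SAP section 2 drops the AE summary by maximum intensity, so no planned AE table would show a grade increase. Intensity remains in the AE listing.
- SAP 4.2.5.2 computes time to progression as AE date minus Day 1 date plus 1. A start one day before dosing gives -1 + 1 = 0, and three days before gives -3 + 1 = -2. The missing dating rule therefore reaches this endpoint too.

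**Where the events still appear**

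- SAEs are defined over any study phase and summarised without a TEAE restriction (SAP 4.2.2.1).
- Cardiovascular events are listed and summarised with their adjudication results, also without that restriction.

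**Scale**

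Inputs: N = 46 (SAP section 2, full analysis set; the Safety Analysis Set is likewise everyone dosed) and the exact Clopper-Pearson 95% interval (SAP 4.2.2.1). The counts are illustrative.

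| Participants counted | Percentage | Exact 95% interval |
|---|---|---|
| 0 of 46 | 0.0% | 0 to 7.7% |
| 1 of 46 | 2.2% | 0.06 to 11.5% |
| 2 of 46 | 4.3% | 0.5 to 14.8% |
| 3 of 46 | 6.5% | 1.4 to 17.9% |

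One omitted child costs 1/46 = 2.2 percentage points of overall incidence. This is a maximum, because incidence counts participants with at least one event: a child with another TEAE is already in the numerator. For AESIs the condition is that the child has no other AESI. The first counted child raises the exact upper limit from 7.7% to 11.5%.

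The SAP also tabulates by cohort and route. There the share is 1/n for a smaller n, which the documents do not give.

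**The case against.** The strongest reply is that the protocol already points towards dating from the worsening, and that little is lost in any case. Much of this stands.

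- *Chronic conditions.* Abnormal findings at screening go to medical history, findings after dosing are AEs (protocol 8.2.1), and aggravated findings are generally reported as AEs (8.3.7). When the AE is the deterioration, its natural onset is after dosing, so it is a TEAE. A reader might infer that decompensation of existing heart disease is routinely lost. The documents do not support that: Cohorts 1 and 2 must be medically stable, and cardiac events have their own adjudicated summary.
- *Serious worsening.* A reader might infer that these events vanish from primary safety reporting. They do not. SAE incidence is itself a primary endpoint, and protocol 8.1.2 says "Severe COVID-19 will be collected and recorded in the eCRF as an SAE".
- *COVID-19 progression as an AESI.* A reader might infer that the TEAE rule keeps progression out of the AESI count. Progression is not on the AESI list in either document, so the rule makes no difference there. It also has its own secondary endpoint through Day 29 (SAP 4.2.5.2).
- *Non-serious Cohort 2 symptoms.* Protocol 8.1.1 keeps most of these out of AE recording by design. A worsening clause would not recover them.
- *A large downward bias.* A reader might scale the Table 5 minima to guess a Cohort 2 size and then assume several affected children. The guess is unstable: 21/52 x 46 = 18.6, but 21/100 x 46 = 9.7. Actual Cohort 2 enrolment is not stated, and no source gives the number who deteriorate with a pre-dose start date.

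What the reply does not remove is the rule itself. It is stated without a worsening clause, and no dating convention in either document ensures that the three kinds of event above receive a post-dose onset.

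**Conclusion.** The point holds in limited form. An AE with a recorded start before dosing that worsens or first becomes serious after dosing is excluded from TEAE incidence by a stated rule, and from AESI incidence if it is of a listed type. The clearest cases are Cohort 2 symptoms that later become serious and events with onset between consent and dosing.

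The loss is confined to the TEAE and AESI counts and is at most 2.2 percentage points of overall incidence per affected child. This assumes a denominator of 46, which is what Table 2 implies by assigning the safety endpoints to the Safety Analysis Set. The text of SAP 4.2.2 instead names the SARS-CoV-2 nAb evaluable set for the summaries; with fewer children in the denominator the share per child would be larger. The documents support neither a total for the children affected nor a claim that the overall safety picture is materially biased. The change is still worth making, because the counts are primary and the remedy is cheap.

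**What to change.** In SAP 4.2.2.1:

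1. Define a TEAE as an AE with onset at or after dosing, or an AE with onset before dosing that first meets a seriousness criterion at or after dosing. The second limb uses a field already collected, "Date AE met criteria for SAE".
2. For non-serious worsening, state that a post-dose increase in grade of an event with pre-dose onset is entered as a new AE with its own onset date. A derivation will not work here, because the AE variables in protocol 8.3.2 include no date of grade change.
3. Apply the same definition to AESIs.
4. Reconcile the start of AE collection between protocol 8.3.1 (dosing) and SAP 4.2.2.1 (consent).

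Cost: a few sentences in the SAP, a small derivation for the seriousness limb, a data-entry instruction to sites, and possibly some queries before database lock. TEAE counts may rise slightly.

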#### Serious Adverse Events

An SAE is an AE occurring during any study phase (ie, run-in, treatment, washout, followup), that fulfills one or more of the following criteria:

- Results in death
- Is immediately life-threatening
- Requires in-participant hospitalization or prolongation of existing hospitalization
- Results in persistent or significant disability or incapacity
- Is a congenital anomaly or birth defect
- Is an important medical event that may jeopardize the participant or may require medical treatment to prevent one of the outcomes listed above

Serious Adverse Events are identified as serious via the eCRF.

#### Adverse Event of Special Interest

An AESI includes any of the following TEAEs (categorized in the eCRF):

- Anaphylaxis
- Hypersensitivity
- Serious Hypersensitivity Reaction including immune complex disease
- Injection Site and Infusion Site Reactions (as identified by the investigator in the Adverse Event eCRF form. For the summary of injection/infusion site inspection, please see Section 4.2.8.2)
- MIS-C

- Thrombotic events, heart failure and cardiac ischemia

### **Cardiovascular Events**

Cardiovascular (CV) AEs are referred to a CV Event Adjudication Committee. Only adjudicated events will be included as AESIs.

CV events (cardiac ischemia, CV death, heart failure, stroke, thrombotic event) with their adjudication results will be listed and summarized:

- Summary of CV adjudication results
- time to onset of the event
- number of participants/events with positive adjudication

Demographics, baseline characteristics and medical history summaries will be repeated for those participants who experienced a positively adjudicated CV event.

### **Analysis of Adverse Events**

The safety of AZD7442 will primarily be assessed by:

- Incidence of TEAEs through end of study
- Incidence of SAEs through end of study
- Incidence of AESIs through end of study

Summaries of these incidences will include the number and percentage of participants reporting at least one event with the 95% exact Clopper-Pearson confidence interval for the percentage, number of events, exposure adjusted rates and presented by cohort and route of administration.

An overview of AEs will be presented for each cohort and route of administration, including the number and percentage of participants with any AE and SAEs. Summaries will present the relationship to IMP as assessed by the Investigator, seriousness, and deaths.

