1.3 Schedule of Activities

Table 1 summarizes the SoA at screening for all participants. **Table 2** and **Table 3** summarize the SoA during the main study for neonates (modified sample collection) and non-neonates, respectively.

Table 1 Schedule of Activities: Screening Period (All Participants)

Procedure/study day	Day -7 to Day 1 ^a	For details, see section:
Informed consent/assent	X	5.1
Assignment SID number ^b	X	6.3
Demographics and risk categorization	X	5.1
Medical history	X	NA
Complete physical examination, including height and weight	X	8.2.1
Vital signs (including pulse oximetry)	X	8.2.2
Triple 12-lead ECG	X	8.2.3
Serum chemistry, hematology, urinalysis ^c	X	8.2.4

Table 1 Schedule of Activities: Screening Period (All Participants)

Procedure/study day	Day -7 to Day 1 ^a		For details, see section:
Coagulation	X		8.2.4
Urine pregnancy test (post-pubertal females only) ^d	X		8.2.4.5
Assessment of SAEs	X		8.3
Concomitant medications	X		6.5
Serum sample for SARS-CoV-2 serology (anti-nucleocapsid) testing (all participants other than neonates)	X		8.5.3.2
Verify eligibility criteria	X		5.1, 5.2
Screening criteria specific to each cohort	Cohort 1 Pre-exposure prophylaxis	Cohorts 2 and 3 Treatment of COVID-19	For details, see section:
Documented SARS-CoV-2 RT-PCR test taken \leq 3 days before Day 1 ^c OR Rapid SARS-CoV-2 antigen test (for assignment to study cohorts) per local standard of care authorized for screening or diagnosis	X (negative)	X (positive)	8.6.1
COVID-19 Symptom screen	NA	X (Yes)	5.1

^a Screening activities may be collected over more than one visit during the 7-day screening window if necessary; if screening and dosing occur at the same visit, only one evaluation is required, unless otherwise specified. The sample taken closest to dosing and prior to dosing is considered the baseline sample.

^b Assigned by the IRT system. See Section [6.3](#) for further information.

^c Collection of urine samples for urinalysis from participants who are unable to provide urine samples is not mandatory provided that a reasonable attempt has been made to collect the samples.

^d If urine tests positive or is indeterminate, a quantitative serum β -hCG will be performed for confirmation before the participant is enrolled in the study. Pregnancy testing is for baseline purposes only, and a participant with a positive urine pregnancy test can still participate in the study.

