8.3.1 Time Period and Frequency for Collecting AE and SAE Information

Adverse events will be collected from the time of IMP administration throughout the study, up to and including the last visit. After IMP administration on Day 1, participants will be monitored on site for a minimum of one hour for general safety, including injection/infusion site reactions and hypersensitivity reactions (including anaphylaxis).

Serious adverse events will be recorded from the time of signing of the ICF throughout the study, up to and including the last visit.

If the Investigator becomes aware of an SAE with a suspected causal relationship to the IMP that occurs after the end of the clinical study in a participant treated by him or her, the Investigator shall, without undue delay, report the SAE to the Sponsor.

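### The SAE incidence and its exposure-adjusted rate are not limited to onset at or after dosing, so a pre-dose SAE in a dosed child would be counted; the expected effect is small.

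*SAP*

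**What the plan says.** **Collection.** Protocol 8.3.1 gives SAEs an earlier start than other events: "Serious adverse events will be recorded from the time of signing of the ICF throughout the study, up to and including the last visit". For AEs in general it says "Adverse events will be collected from the time of IMP administration throughout the study, up to and including the last visit". The screening table in protocol 1.3 has a row for "Assessment of SAEs" covering Day -7 to Day 1. SAP 4.2.2.1 starts all AE collection at consent: "Adverse Events will be collected throughout the study from date of informed consent until the end of the follow-up".

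**Definitions.** SAP 4.2.2.1 states that "Treatment-emergent AEs are those AEs with onset date/time at or after dosing". The SAP defines AESIs as a list of TEAEs, so they inherit that limit. For SAEs it says instead that "An SAE is an AE occurring during any study phase (ie, run-in, treatment, washout, followup", and it identifies them by the seriousness flag in the eCRF.

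**Analysis.** The SAP's Analysis of Adverse Events lists TEAEs, then "Incidence of SAEs through end of study", then AESIs. Each gets the number and percentage of participants, an exact 95% interval, the number of events and exposure-adjusted rates, by cohort and route. The AE overview in the same section also counts SAEs without a treatment-emergent limit. Protocol 9.4.4 words the SAE measure in the same way and adds no restriction.

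**The concern.** SAEs are part of a primary safety endpoint. An event that began before the single dose cannot have been caused by it, yet the written rule would place it in the same summary as post-dose events. The three primary incidences would then cover different periods, and a child could appear in the SAE row without appearing in the TEAE row beside it.

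The exposure-adjusted rate has a further problem. The SAP does not say when exposure time starts. If it is counted from dosing, a pre-dose SAE adds to the numerator while the time in which it arose adds nothing to the denominator. With enrolment stopped at 46 dosed children and results split by cohort and route, one event is visible.

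**Working it through.** **1. Does any text remove pre-dose SAEs from the summary?**

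| Measure | Onset limit in the SAP | Pre-dose event counted? |
|---|---|---|
| TEAE | At or after dosing | No |
| AESI | Defined as TEAEs | No |
| SAE | Any study phase, including run-in | Yes, as written |

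The Safety Analysis Set (SAP Table 1) keeps only dosed participants. That removes screen failures but does not filter events by onset. SAP 3.3.5 assigns AEs that start at or after dosing to treatment, but this is a rule for missing start dates and does not limit the SAE summaries. The same section allows for AEs that ended before dosing, so such events are expected in the data. No text closes the gap.

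**2. How long is the pre-dose period?** Protocol 4.1 gives a maximum participation of 388 days. This reproduces as 7 screening days + 366 + a 15-day visit window = 388. Screening is therefore at most about 7 days, or 7/(7 + 366) = 1.9% of planned observation. Footnote a of the screening table allows screening and dosing at the same visit. In the other direction, protocol 5.4 allows one rescreening without new consent, so a rescreened child could have a longer interval from consent. The documents do not say how many such children there are.

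**3. Effect on the incidence.** SAP Section 2 gives 46 dosed participants. Exact (Clopper-Pearson) intervals for assumed counts, where the extra child has no post-dose SAE:

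| Post-dose SAE participants | As written, plus one pre-dose only | Limited to onset at or after dosing |
|---|---|---|
| 0 | 1/46 = 2.2% (0.1 to 11.5) | 0/46 = 0% (0 to 7.7) |
| 4 | 5/46 = 10.9% (3.6 to 23.6) | 4/46 = 8.7% (2.4 to 20.8) |

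The shift is 1/46 = 2.2 points overall. In a cohort-by-route cell it is 1/n. Cell sizes are not given; with an assumed 10 children it would be 10 points.

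**4. Effect on the rate.** Assume 366 days per child counted from dosing: 46 × 366/365.25 = 46.1 person-years. With one event per affected child, 4/46.1 = 8.7 and 5/46.1 = 10.8 per 100 person-years. If the 7 screening days were added to the denominator, the second figure would be 5/47.0 = 10.6.

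**5. How likely is such an event?** The documents give no background SAE rate. Assume a constant 0.05 to 0.5 per child-year. The expected count is 46 × (days/365.25) × rate, and the chance of at least one is 1 − exp(−expected).

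| Assumed days from consent to dosing | Expected pre-dose SAEs | Chance of at least one |
|---|---|---|
| 1 for every child | 0.006 to 0.063 | 0.6% to 6% |
| 7 for every child | 0.04 to 0.44 | 4% to 36% |

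The 7-day row takes the maximum window for all 46 children. Both rows ignore selection by the eligibility criteria and so lean high.

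**The case against.** The strongest reply is that the SAP is silent rather than wrong. Its objective is safety after a single dose, and detailed presentation rules are left to a table-shell document that is not public and may apply an onset filter. The measure repeats protocol 9.4.4, and reporting every recorded SAE alongside relatedness is a defensible convention. All analyses are descriptive. The AE listing shows start date and time, time from dose, seriousness and relatedness, so a reader could identify a pre-dose SAE.

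Eligibility also works against the event. Cohort 3 is empty. Cohorts 1 and 2 require stable underlying disease and, with limited exceptions, no current need for hospital or emergency care. Cohort 1 also excludes significant acute illness around the day of dosing. Eligibility is checked again on Day 1. Pre-planned admissions for existing illness that has not unexpectedly worsened are not AEs (Appendix B 2).

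Much of this stands as to size. It does not remove the point. The SAE definition names run-in expressly, and the neighbouring measures carry the limit that this one lacks. An unseen shell cannot stand in for a rule in the SAP, and a listing does not correct a summary percentage. The exceptions to the hospital exclusion, for neonates in their birth stay and children admitted for maintenance chemotherapy, leave some room for such an event.

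**Conclusion.** The point holds as a minor specification defect. Followed as written, the SAP counts a dosed child's pre-dose SAE in a primary safety incidence, its exact interval and its event count. The expected effect is small; the realised effect is 2.2 points overall for each child whose only SAE is pre-dose, and zero if no such child exists. The 46-child denominator assumes the Safety Analysis Set, as in SAP Table 2. The text of SAP 4.2.2 names the neutralizing-antibody set instead, which would be no larger.

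A reader might infer three stronger things that the documents do not support:

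- That a pre-dose SAE occurred or is likely. No such event is reported, no background rate is given, and the higher chances above need the full 7-day window for every child with no selection.
- That the rate certainly mismatches numerator and denominator. Exposure time is undefined, so the mismatch is possible but not established.
- That every pre-dose SAE raises the percentage. A child who also has a post-dose SAE is already counted; only the event count changes.

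**What to change.** In the SAP's Analysis of Adverse Events, replace the SAE measure with the incidence of treatment-emergent SAEs (onset at or after dosing) through end of study. Apply the same limit in the AE overview and the exposure-adjusted rates. Define exposure time as running from dosing to end of follow-up. List SAEs with onset between consent and dosing separately.

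Because protocol 9.4.4 uses the unrestricted wording, record the change in SAP Section 2. The cost is one SAP edit, a note in Section 2, an onset filter in the affected tables and one short listing. Data collection is unchanged and no safety information is lost.
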